13.4. Stratification Factors

N/A

13.5. Analysis of Secondary Endpoints

PK and PD analysis

Descriptive statistics will be provided for selected PK, and PD data by dose and time as appropriate. Descriptive statistics on continuous data will include means, medians, standard deviations, and ranges, while categorical data will be summarized using frequency counts and percentages. Graphical summaries of the data may be presented.

A full pharmacokinetic profile of KRT-232 (AMG 232) will be proposed in this protocol to assess exposure-response relationships with various PD endpoints (i.e., MIC-1 changes, toxicity, efficacy). KRT-232 (AMG 232) concentrations in these samples will be quantitatively measured using liquid chromatography/tandem mass spectrometric (LC/MS/MS) method that will be developed by the Analytical Pharmacology Core Laboratory at the Sidney Kimmel Comprehensive Cancer Center (SKCCC) at Johns Hopkins. For KRT-232 (AMG 232), the individual PK parameters from a single dose will be estimated for C_{max} , AUC, $T_{1/2}$, apparent Cl/F, and apparent V/F using non-compartmental or compartmental PK methods with the software WinNonlin. For serum MIC-1 levels, each individual level will be normalized to the baseline level for that subject. Advanced population PK methods may be employed to assess the link between drug exposure and biological effects and efficacy. The PK variables and changes in MIC-1 will be tabulated and descriptive statistics (e.g., geometric means and coefficients of variation) calculated for each dose level. PK parameters (i.e., $T_{1/2}$, Cl, and AUC) and MIC-1 changes will be compared across dose level using nonparametric statistical testing techniques. Exploratory correlative studies with pharmacodynamic (biological endpoints, toxicity and efficacy) will be analyzed using nonparametric statistics. Significance for comparisons will be at the $p<0.05$ level.

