2.6. Rationale of KRd + KRT-232 (AMG 232) Human Dosing

Dosing for the KRd backbone for the current proposed study is modeled after the Phase 3 ASPIRE study as described in Section 2.4, which was based on an earlier Phase 1 study where the MTD was not reached for KRd dosing (Niesvizky et al., 2013). Hence, KRd at these dose levels (carfilzomib 27 mg/m², lenalidomide 25 mg, and dexamethasone 40 mg) has an acceptable and well-studied safety profile. In practice, carfilzomib is often given at higher doses (36 mg/m²) in combination with lenalidomide and dexamethasone, based on a phase 1/2 study of KRd in newly diagnosed multiple myeloma (Jakubowiak et al., 2012), which gives added confidence that the addition of KRT-232 (AMG 232) to the KRd backbone at its standard dosing will be feasible from a safety and tolerability standpoint.

Although the MTD of KRT-232 (AMG 232) was defined at 240 mg QD for 7 days on a 21-day cycle in the first-in-human (FIH) study of KRT-232 (AMG 232) in solid tumors (Section 2.2), the starting dose level of KRT-232 (AMG 232) for the current study will begin at 60 mg 7 days on a 28-day cycle to carefully evaluate for overlapping toxicities such as thrombocytopenia with the KRd backbone. Dose-escalation will occur using a standard 3+3 design with increasing dose levels of KRT-232 (AMG 232) at 90 mg, 120 mg, 180 mg, and 240 mg 7 days on a 28-day cycle, with the highest planned dose level 5 being comparable to the MTD in the first-in-human trial of KRT-232 (AMG 232) monotherapy. Using this standard 3+3 design, a DLT rate less than 33% would be considered acceptable.

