2.7.2. Pharmacokinetic and Pharmacodynamic Studies

Macrophage inhibitor cytokine-1 (MIC-1)

MIC-1, a secreted p53 transcriptional target, will be evaluated as an integrated pharmacodynamic biomarker for p53 pathway activation in response to MDM2 inhibition in this study. In preclinical studies, increases in MIC-1 levels were observed *in vitro* and *in vivo* in response to doxorubicin treatment, and correlated with increases in other downstream markers of p53 pathway activation (Yang et al., 2003).

In a clinical study with the MDM2 inhibitor RG7112 in liposarcoma, serum MIC-1 was been assessed as a pharmacodynamic marker using an ELISA at different time points and correlated with drug exposure levels of the study drug (Ray-Coquard et al., 2012). In preliminary analyses of clinical trial data, there was an exposure-response correlation observed between changes in serum MIC-1 levels and KRT-232 (AMG 232) exposure (both maximal (C_{max}) and total exposure (AUC) (KRT-232 (AMG 232) Investigators Brochure Date: 08 Dec. 2015).

In this study, serum MIC-1 testing will be performed using an ELISA-based assay at the ETCTN central laboratory of [name] at Johns Hopkins University. For serum MIC-1 levels, each individual level will be normalized to the baseline level for that subject collected prior to KRT-232 (AMG 232) dosing.

KRT-232 (AMG 232) pharmacokinetic profile

These studies are necessary to characterize the exposure to KRT-232 (AMG 232). KRT-232 (AMG 232) is an orally bioavailable MDM2 inhibitor. In cancer subjects, KRT-232 (AMG 232) exposure is dose proportional over the dose range proposed in this LOI (KRT-232 (AMG 232)

Investigators Brochure Date: 08 Dec. 2015). [REDACTED]

In this protocol, KRT-232 (AMG 232) will be combined with carfilzomib, lenalidomide, and dexamethasone. Carfilzomib is primarily inactivated by peptidases and hydrolysis with minor contributions by CYP450 isozymes (specific isozyme not listed). Lenalidomide is not metabolized by CYP450 but is a P-glycoprotein substrate. Dexamethasone is metabolized by CYP3A4 but does not have a narrow therapeutic window. Therefore concerns of a drug-drug interaction are minimal with the combination. Other narrow therapeutic window drugs predominantly cleared by CYP2C8 and/or CYP3A4 will be excluded.

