KRT-232 (AMG 232) drug-exposure measurements will be quantitatively measured using liquid chromatography/tandem mass spectrometric (LC/MS/MS) method that will be developed by the Analytical Pharmacology Core Laboratory at the Sidney Kimmel Comprehensive Cancer Center (SKCCC) at Johns Hopkins in collaboration with [name]. For KRT-232 (AMG 232), the individual PK parameters from a single dose will be estimated for C_{max} , AUC, $T_{1/2}$, apparent Cl/F, and apparent V/F using non-compartmental or compartmental PK methods with the software WinNonlin. Advanced population PK methods may be employed to assess the link between drug exposure and biological effects and efficacy. The PK variables and changes in MIC-1 will be tabulated and descriptive statistics (e.g., geometric means and coefficients of variation) calculated for each dose level. PK parameters (i.e., $T_{1/2}$, Cl, and AUC) and MIC-1 changes will be compared across dose level using nonparametric statistical testing techniques. Exploratory correlative studies with pharmacodynamic (biological endpoints, toxicity and efficacy) will be analyzed using nonparametric statistics. Significance for comparisons will be at the $p < 0.05$ level.

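### The across-dose comparison of AUC carries no stated dose-normalisation, so its p-value mainly reflects assigned dose; proportionality under KRd is tested only implicitly and inefficiently, through Cl/F

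*Combined protocol and SAP*

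**What the plan says.** Section 13.5 sets the PK comparison: "PK parameters (i.e., $T_{1/2}$, Cl, and AUC) and MIC-1 changes will be compared across dose level", by nonparametric tests. The threshold follows: "Significance for comparisons will be at the $p<0.05$ level". Section 2.7.2 and the synopsis (Statistical Considerations) repeat the plan. No particular test is named. No dose-normalisation of AUC and no dose-proportionality model appears in any of these places or in the analysis paragraph of section 9.3.1.

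The clearance that is estimated is the apparent one: section 13.5 lists "apparent Cl/F, and apparent V/F using non-compartmental or compartmental PK methods with the software WinNonlin". Cmax is also estimated, and PK variables are tabulated by dose level, but Cmax is not in the list of parameters to be compared.

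On prior knowledge, section 2.7.2 states that "KRT-232 (AMG 232) exposure is dose proportional over the dose range proposed in this LOI". Section 2.6 starts escalation at 60 mg and then has "increasing dose levels of KRT-232 (AMG 232) at 90 mg, 120 mg, 180 mg, and 240 mg 7 days on a 28-day cycle". PK sampling is a single-dose profile on Cycle 1 Day 1, up to 24 hours (section 9.3.1.1), in both parts of the study (sections 10.1 and 10.2). KRd also starts on that day, so the profile is taken under the combination.

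**The concern.** A test of equal AUC across levels has a null hypothesis that the protocol itself says is false. If it rejects, that restates the dose assignment. If it does not, that reflects small cohorts or high variability. Neither outcome says anything about how the drug behaves with KRd.

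The informative question is whether exposure stays proportional to dose when KRT-232 is given with KRd. The plan reaches it only through Cl/F, with an unnamed nonparametric comparison and no interval. If that comparison is non-significant in cohorts of 3 to 6, a reader could take it as evidence of linearity when the data could not have shown otherwise. Exposure-response, including toxicity, is a secondary objective in both parts (sections 1.1.2 and 1.2.2), so it is worth describing the dose-exposure relation well. Section 2.7.2 links MIC-1 changes to Cmax as well as AUC, yet Cmax is outside the planned comparison.

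**Working it through.** The plan gives no power or effect size for this comparison, so there is no figure to reproduce.

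**Inputs from the documents.** Doses 60, 90, 120, 180 and 240 mg (sections 2.6 and 5.4); 3 to 6 subjects per level and a goal of 10 in expansion (section 13.3); at least 6 at the recommended phase 2 dose (section 5.6), hence about 6 + 10 = 16 there; threshold 0.05 (section 13.5).

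**Assumptions.** AUC is log-normal. Between-subject CV is 30%, 50% or 70%, because no variability figure is visible (clinical PK text is partly redacted). The nonparametric comparison is taken as Kruskal-Wallis. The LOI dose range in section 2.7.2 is taken to cover the protocol doses.

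**Step 1: what proportionality implies for raw AUC.** Median AUC differs by 240/60 = 4-fold between the lowest and highest levels. Simulated Kruskal-Wallis rejection rates on raw AUC under exact proportionality:

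| Subjects per level | CV 30% | CV 50% | CV 70% |
|---|---|---|---|
| 3, 3, 3, 3, 3 | 94% | 49% | 26% |
| 6, 6, 6, 6, 6 | 100% | 98% | 84% |
| 3, 3, 3, 3, 16 | 100% | 97% | 78% |
| 3, 3, 16 (stops at 120 mg) | 84% | 41% | 24% |

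A trend test on raw AUC with 3 per level rejects in 100%, 93% and 75% of trials.

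**Step 2: what the Cl/F comparison tests.** Cl/F = dose/AUC, so Cl/F is the reciprocal of AUC/dose. A rank test gives the same p-value for both, and did so in every simulated trial. Under proportionality it rejects in about 2-5% of trials. The identity is exact for the AUC from which Cl/F is derived (AUC to infinity). It is only approximate if the reported AUC stops at 24 hours, and the plan does not say which AUC it means.

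**Step 3: power against non-proportionality.** Take AUC proportional to dose^1.4. Dose-normalised exposure at 240 mg is then 4^0.4 = 1.74 times that at 60 mg. The slope test regresses log(AUC) on log(dose) and tests slope = 1.

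| Subjects per level | Omnibus Cl/F test, CV 30% / 50% | Slope test, CV 30% / 50% |
|---|---|---|
| 3, 3, 3, 3, 3 | 18% / 7% | 68% / 33% |
| 3, 3, 3, 3, 16 | 60% / 24% | 93% / 58% |
| 3, 3, 16 (stops at 120 mg) | 17% / 10% | 31% / 16% |

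**Step 4: width of the slope interval.** Half-width = t × σ / √Sxx, with σ = √ln(1 + CV²) = 0.294 at CV 30% and 0.472 at CV 50%. Sxx is the sum of squared deviations of log dose.

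- 3 per level: squared deviations 0.514 + 0.097 + 0.001 + 0.146 + 0.448 = 1.205 per set of five; × 3 = 3.616. With t(13) = 2.160: 2.160 × 0.294 / 1.902 = 0.33, and 2.160 × 0.472 / 1.902 = 0.54. The simulated averages are 0.33 and 0.53, because the estimated SD runs slightly below the true one.
- 3, 3, 3, 3, 16: Sxx = 6.738 and t(26) = 2.056 give 0.23 and 0.37.
- 3, 3, 16: Sxx = 1.296 and t(20) = 2.086 give 0.54 and 0.86.

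**The case against.** A reader might infer that dose linearity under KRd is not tested at all. The documents do not support that. Section 13.5 lists clearance beside AUC, the clearance is Cl/F, and its rank comparison across doses is a test of proportionality on data collected with KRd.

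A reader might also infer that a significant AUC result is built in. That is too strong. It is close to certain with full escalation plus expansion at CV 30-50%. It is about even with 3 per level at CV 50%, and about one in four at CV 70% or if escalation stops at 120 mg with that CV. The accurate statement is that the result is uninformative whichever way it falls.

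Nor does it follow that a real departure would be missed. Three subjects at every level cannot be the final dataset, because the chosen dose must have at least 6 and expansion aims to add 10. With 3, 3, 3, 3 and 16 the Cl/F test has 60% power at CV 30%. If escalation stops at 120 mg, the slope test is weak too.

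The defence is also right that proportionality is not a named objective. Exposure-response has its own analyses in section 13.5, and escalation rests on DLT counts alone (sections 5.4 and 5.6). The plan says only that parameters are compared; a test of equal raw AUC is the natural reading, but it is an inference. An ordered rank test of Cl/F would use dose order, so the power gap in Step 3 applies to the omnibus reading. On Cmax, tabulation by dose level is already planned; what is missing is any assessment of its relation to dose.

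What remains is that the raw-AUC test serves no purpose, and that the planned test of proportionality is implicit, unnamed, without an interval, and less powerful than a slope analysis of the same samples in every design examined.

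**Conclusion.** The point holds in limited form. As written, the AUC comparison in section 13.5 mainly reports the assigned dose. Proportionality under KRd is tested, but only through Cl/F. For AUC rising as dose^1.4 and CV 30%, the slope analysis gains 50 percentage points of power with 3 per level (68 - 18), 33 with 3, 3, 3, 3 and 16 (93 - 60), and 14 if escalation stops at 120 mg (31 - 17). At CV 50% the gains are 26, 34 and 6 points.

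These figures rest on the assumed CVs, an illustrative exponent, log-normal exposure and an omnibus rank test. The conclusion about raw AUC does not depend on them; it follows from the protocol's own statement of proportionality. The consequence is confined to secondary PK reporting.

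**What to change.** In section 13.5, section 2.7.2 and the synopsis:

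1. Remove the across-level test of raw AUC.
2. State which AUC is reported and which is used to derive Cl/F.
3. Fit a power model, log(AUC) and log(Cmax) on log(dose), and report each slope with its 95% confidence interval against 1.
4. Tabulate dose-normalised AUC and Cmax by level, and keep half-life and Cl/F descriptive.

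The cost is a wording change and one regression per parameter, with no new samples or visits. The model assumes a log-linear relation, and the interval will be wide in small cohorts (Step 4). That width should be reported, since it shows how little a null result would prove.

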13.6. Efficacy Analysis

Efficacy analysis will be performed for all subjects in the dose escalation and dose expansion part of the study. Separate efficacy analyses will be performed on the *full analysis set* which includes all subjects enrolled on study, and the *primary analysis set* which includes only subjects who were biomarker positive (*TP53* WT). Parameters assessed will include minimal residual

disease (MRD) negative, stringent complete response (sCR), complete response (CR), very good partial response (VGPR), and partial response (PR), minimal response (MR) and stable disease (SD) per IMWG Uniform Response criteria. In addition, overall response rate (defined as greater than or equal to PR across all cycles of treatment), response duration, time-to-response (TTR), PFS, and OS will be assessed.

Best overall response categories will be tabulated by dose cohort and overall for the IMWG categories of MRD-negative, sCR, CR, VGPR, PR, MR, SD, progressive disease. A two-sided 95% exact binomial CI will be calculated for each category. The myeloma response rate (responses \geq PR) will also be tabulated by dose cohort and overall. Time-to-event analyses will be done using Kaplan-Meier analyses and will include time to response, duration of response, progression-free survival (PFS), and overall survival (OS), as data allow. If there is not enough data to apply the Kaplan-Meier test, the data will be summarized by descriptive statistics.

Time to response (for responders only) will be calculated as the time from the date of first study treatment dosing to the first date of documented response (PR or better) based on IMWG uniform response criteria. Time to response will be summarized by descriptive statistics by dose cohorts.

Duration of response (for responders only) is defined as the time from the earliest date of documented response (PR or better, based on IMWG uniform response criteria) to the earliest date when disease progression was confirmed. Subjects who are non-responders will be excluded from this analysis. Detailed censoring rules for duration of response will be specified in the SAP.

PFS will be calculated as the time from the time of enrollment until documented disease progression, as determined by the Investigator using IMWG uniform response criteria, or death from any cause, whichever occurs first. Kaplan-Meier methods will be used to estimate PFS over time and the median duration of PFS. Subjects with no PFS event will be censored at the date of their last myeloma disease assessment.

OS is defined as the time from the initial administration of KRT-232 (AMG 232) + KRd to death from any cause. Kaplan-Meier methods will be used to estimate the OS function. Subjects who do not die will be censored at the date that the subject was last known to be alive.

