4.3.2. Subject Enrollment Instructions

- Sites must reserve a slot in Theradex IWRS. Each site is allowed 1 slot reservations at a time with a 5 day guaranteed hold for each slot.
- Next, fax the following redacted documents for review:
 1. Latest clinic note
 2. Pathology report showing histologically confirmed diagnosis of multiple myeloma
 3. Documentation of measurable disease (defined by at least one of the following):
 - a. Serum monoclonal protein M-protein level ≥ 0.5 g/dL
 - b. Urinary M-protein excretion of ≥ 200 mg over a 24-hour period
 - c. Involved free light chain level ≥ 10 mg/dL, along with an abnormal free light chain ratio
- Fax to: [name]/[name] at [contact]. Include your contact information in the fax cover sheet.
- Each reservation will need to be authorized and approved by an MD Anderson designee prior to registering the patient in OPEN. Once the slot is approved in IWRS, you may proceed with registering your patient in OPEN.

There is a two-step process to enrollment in CTSU OPEN. The subject cannot be fully registered in CTSU OPEN without knowledge of the TP53 mutation status which is part of the **eligibility** criteria 3.2.2. However, a patient may begin Cycle 1 of therapy provided they meet all other eligibility criteria aside from criteria 3.2.2.

The two-step enrollment process is as follows:

- (1) Register in CTSU OPEN **Step 1 once slot is approved through Theradex IWRS** to obtain patient's unique study ID
- (2) Subject may begin Cycle 1 therapy after eligibility is established even if TP53 mutation

status is not yet known as per **eligibility** criteria 3.2.2

(3) Study site receives *TP53* results during Cycle 1 therapy (or before) with 2 possibilities below:

- a) If non-wild-type (WT) *TP53* results, the patient is withdrawn from protocol for not meeting eligibility criteria prior to cycle 2 therapy. The site will need to complete step 2 of OPEN to indicate the patient has failed eligibility.
- b) If wild-type (WT) *TP53* results meeting eligibility criteria, the patient can continue on protocol. The site will complete step 2 of OPEN to indicate that patient has met eligibility prior to commencing cycle 2 therapy.

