4.4. General Guidelines

Following registration, subjects should begin protocol treatment within 14 days. Issues that would cause treatment delays should be discussed with the Principal Investigator. If a subject does not receive protocol therapy following registration, the subject's registration on the study may be canceled. The Study Coordinator should be notified of cancellations as soon as possible.

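### PFS is timed from enrollment but OS and time to response from first dose, so in a dosed-only analysis set a subject's PFS can exceed their OS by the registration-to-dose lag

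*Combined protocol and SAP*

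**What the plan says.** Section 13.6 uses two time origins for outcomes that it analyses together.

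- **PFS:** "PFS will be calculated as the time from the time of enrollment until documented disease progression", with the event completed by "or death from any cause, whichever occurs first".
- **OS:** "OS is defined as the time from the initial administration of KRT-232 (AMG 232) + KRd to death from any cause".
- **Time to response:** "the time from the date of first study treatment dosing to the first date of documented response".

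The gap between the two origins is addressed in Section 4.4: "Following registration, subjects should begin protocol treatment within 14 days". This is worded as a target, not a hard limit.

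Section 13.1.2 restricts the full analysis set to subjects who received some KRT-232 and had at least one disease assessment after baseline. The primary analysis set (13.1.3) is the biomarker-positive part of that set. Section 13 gives no reason for starting PFS earlier than the other two outcomes.

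**The concern.** PFS should never be longer than OS in the same subject, because death ends both. With an earlier origin for PFS that ordering can fail, and a listing of individual times could show it.

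The enrollment origin also does not fit the population analysed. A subject who dies between enrollment and first dose never enters the full analysis set. Everyone in the set has therefore survived that interval by construction, and counting it lengthens PFS without any matching risk of death. At stake are the coherence of the PFS and OS curves when read together, and a slight upward shift in the PFS median that 13.6 commits to estimating.

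**Working it through.** The plan states no figure for PFS or OS (no event count, test or sample size), so there is nothing to reproduce. The check is date arithmetic.

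**Inputs**
- E = enrollment date, the PFS origin (13.6). Section 4.3.1 makes OPEN Step 1 the act of enrolling, and Section 3.2.2 lets a patient be enrolled and start treatment before the TP53 result. E therefore falls before dosing.
- D = date of first dose, the origin for OS and time to response (13.6).
- L = D − E, nominally 0 to 14 days (4.4).
- P = date of progression; X = date of death.
- 26.3 months = median PFS in the KRd arm of the earlier phase 3 trial (2.4.3), used only for scale.
- One month = 30.4375 days.

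**Step 1. Death without progression.** PFS = X − E and OS = X − D, so PFS − OS = D − E = L. For a death 100 days after first dose:

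| L (days) | PFS (days) | OS (days) | PFS − OS (days) |
|---|---|---|---|
| 0 | 100 | 100 | 0 |
| 7 | 107 | 100 | 7 |
| 14 | 114 | 100 | 14 |

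**Step 2. Progression, then death.** PFS − OS = (P − E) − (X − D) = L − (X − P). This is positive only when progression precedes death by less than L days. The reversal is therefore mainly a matter of deaths without progression.

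**Step 3. Pre-dose time.** Under 13.1.2 every analysed subject reached D, so none can have died between E and D. Each PFS time, whether event or censored, carries its own L of time free of death. If all subjects had the same L, the whole Kaplan-Meier PFS curve would move right by L.

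**Step 4. Size.** 14 / 30.4375 = 0.46 months, and 0.46 / 26.3 = 0.017, or 1.7%.

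**Step 5. With first dose as the common origin.** Death without progression gives PFS − OS = 0. Progression before death gives PFS − OS = −(X − P), which is never positive. The reversal cannot occur.

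**The case against.** **It hardly matters in this trial.** PFS and OS appear in no objective in Section 1. They are estimated descriptively, as far as the data allow, in a single-arm phase 1 study. Response is assessed every 4 weeks (11.1), so a 14-day lag is at most half an assessment interval. No dose decision depends on it. All of this stands and sets the severity. It does not make the two origins consistent.

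**A first-dose origin is undefined for a subject who is never dosed.** Section 13.6 describes the full analysis set as everyone enrolled, which conflicts with 13.1.2. This stands in part: the fix has to name the 13.1.2 definition. It does not favour the present text, since an undosed subject already has no OS origin.

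**A larger problem might be inferred, but the documents do not support it.** Section 4.3.2 says "There is a two-step process to enrollment in CTSU OPEN" and adds: "The subject cannot be fully registered in CTSU OPEN without knowledge of the TP53 mutation status". A reader might conclude that enrollment could mean Step 2, as late as the start of Cycle 2. Adding the 14-day window to a 28-day Cycle 1 would then leave the PFS origin open by 42 days, or six weeks. Several places rule this out:
- Sections 4.3.1 and 3.2.2 place enrollment at Step 1, before the TP53 result.
- Section 8.1 has sites order KRT-232 once enrollment is confirmed, so enrollment precedes dosing.
- Section 13.1.4 keeps subjects removed for a TP53 mutation or deletion eligible for a set made up of enrolled subjects.

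The 42 days is thus a distance between two readings, one of which fails. It is not an error carried by any subject's PFS. The two effects also pull in opposite directions: a Step 2 origin during Cycle 1 would shorten PFS, not lengthen it beyond OS.

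**Conclusion.** The point holds at low severity. In 13.6 PFS starts at enrollment, while OS and time to response start at first dose. For a subject who dies without progression, PFS exceeds OS by the registration-to-dose lag: nominally 0 to 14 days, up to about 0.46 months, or 1.7% of the quoted 26.3-month median. The same lag adds time to PFS that is guaranteed free of death.

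This rests on three assumptions: enrollment means OPEN Step 1; the 13.1.2 definition of the full analysis set governs; and sites keep to the 14-day target. A later start would widen the gap day for day. Section 13.6 defers only the censoring rules for duration of response to the SAP, so nothing in the text indicates that the PFS origin will be settled elsewhere.

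**What to change.** In Section 13.6, define PFS as running from the date of first study treatment dose to documented progression or death, the same origin as OS and time to response. State that it is analysed in the full analysis set as defined in 13.1.2, and bring the description of that set in 13.6 into line.

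The cost is close to nothing: one sentence on the origin plus the cross-reference. No visit, data item, sample size or clinical rule changes. Reported PFS becomes shorter by each subject's lag, up to about two weeks within the window.
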